6. SELECTION AND WITHDRAWAL OF SUBJECTS

6.1. Subject Inclusion Criteria

Each subject must meet all of the following inclusion criteria to be enrolled in the study:

- Adult (age \geq 18 years)
- Able to provide written informed consent
- Histologically confirmed diagnosis of DLBCL, NOS, including DLBCL arising from low-grade lymphoma (ie, an indolent pathology such as follicular lymphoma, or marginal zone lymphoma transforming into DLBCL)
- Subjects must have CD20+ and CD19+ lymphoma based on flow cytometric or immunohistochemical evaluation of their most recent biopsy
- At a minimum, archival paraffin embedded tumor tissue (preferred) or unstained slides must be available for retrospective cell of origin determination by a central independent pathologist. Subjects will be consented and may undergo an optional (recommended) biopsy to obtain fresh tumor tissue if a peripheral disease site can easily and safely be accessed. A fresh tumor tissue sample will satisfy this criterion for those subjects who do not have adequate archival tumor tissue; in this case, the fresh tumor biopsy becomes mandatory for participation.
- Subjects must have at least 1 of the following:
 - Relapsed disease after standard therapeutic options, as defined below:
 - Documented PD, according to the Lugano 2014 criteria ([Cheson, 2014](#)) after the most recently administered anti-lymphoma regimen
 - Primary refractory DLBCL, defined as follows:
 - Documented persistent disease (less than a complete remission [PR, SD, or PD], according to the Lugano 2014 criteria [[Cheson, 2014](#)]) at the completion of first-line therapy, or
 - Progressive disease (according to the Lugano 2014 criteria) within 3 months of completion of first-line therapy
- Subjects must have received at least 1 prior systemic line(s) of therapy, one of which must have included multi-agent chemoimmunotherapy that includes an anti-CD20 monoclonal antibody. DLBCL arising from low-grade lymphoma must have relapsed or refractory disease after at least 2 prior lines of chemoimmunotherapy (at least one of which must have been directed at the DLBCL arising from low grade lymphoma).
- At least 1 bidimensionally measurable disease site. The lesion must have a greatest transverse diameter of \geq 1.5 cm and greatest perpendicular diameter of \geq 1.0 cm at

baseline. The lesion must have a positive finding on PET scan (for definition, see [Cheson, 2014](#)).

- Subjects who are ineligible for or refuse hematopoietic stem cell transplantation (HSCT). Subjects may be considered ineligible for HSCT for any of the following reasons (Documentation of the reason for a subject's ineligibility must be provided in the subject's source data and electronic case report form [eCRF]):
 - Age
 - Performance status
 - Comorbidities
 - Stem cell mobilization failure
 - Failure of prior transplant
 - Insufficient response to salvage chemotherapy
 - Subject refusal
 - Logistical reasons
 - Other potential reasons not listed above will be considered on a case-by-case basis
- If eligible for CAR-T therapy, subjects must consent to bypassing the approved treatment with demonstrated clinical benefit
- An Eastern Cooperative Oncology Group (ECOG) performance status of 0 to 2 (see [Appendix A](#))
- Completed vaccination for the SARS-CoV-2 virus prior to study entry is recommended

Laboratory Values

- Subjects must meet the following laboratory criteria at screening:
 - $ANC \geq 1.5 \times 10^9/L$ (for subject with bone marrow involvement $ANC \geq 0.5 \times 10^9/L$)
 - Platelet count $\geq 90 \times 10^9/L$ (for subjects with bone marrow involvement platelet count $\geq 50 \times 10^9/L$)
 - Total serum bilirubin $\leq 1.5 \times$ upper limit of normal (ULN), unless secondary to Gilbert's syndrome or documented liver involvement by lymphoma. Subjects with Gilbert's syndrome or documented liver involvement by lymphoma may be included if their total bilirubin is $\leq 5 \times$ ULN

- ALT, AST, and alkaline phosphatase $\leq 3 \times$ ULN, or $< 5 \times$ ULN in cases of documented liver involvement
- Serum creatinine clearance must be ≥ 60 mL/minute calculated using a standard Cockcroft and Gault formula or Modification of Diet in Renal Disease (MDRD; [Levey, 1999](#))
- Willingness to avoid pregnancy or fathering children based on the criteria below.
 - Male subjects with reproductive potential must agree to take appropriate precautions to avoid fathering children (with at least 99% certainty) from screening through 180 days (6 months) after the last dose of study treatment, even if they have undergone a successful vasectomy, and must refrain from donating sperm during this period. Permitted methods that are at least 99% effective in preventing pregnancy (see [Section 6.4](#)) should be communicated to the subjects and their understanding confirmed.
 - Women of childbearing potential subjects:
 - Must commit either to abstain continuously from heterosexual sexual intercourse or agree to take appropriate precautions to avoid pregnancy (by using 2 different methods of birth control with at least 99% certainty) starting at least 4 weeks before taking the study treatment, while taking the study treatment, during breaks (dose interruptions), and for at least 8 months after stopping the study treatment. Permitted methods that are at least 99% effective in preventing pregnancy (see [Section 6.4](#)) should be communicated to the subjects and their understanding confirmed.
 - Must have a negative serum pregnancy test at screening (within 10 to 14 days of Day –8) and before the first dose of lenalidomide on Day 1 (within 24 hours of initiating treatment with lenalidomide).
 - Agree to ongoing pregnancy testing during the course of the study: weekly during the first month of study drug treatment, then monthly thereafter for women with regular menstrual cycles or every 2 weeks for women with irregular menstrual cycles (even if true abstinence is the chosen method of birth control) up to and including the end-of-treatment (EOT) visit.
 - Must refrain from breastfeeding and donating oocytes during the course of study and for 8 months after the last dose of study treatment.

Note: The subjects should be informed about the option of donation and cryopreservation of germ cells before the study if applicable.

- In the opinion of the Investigator, the subjects must:
 - Be able and willing to receive adequate prophylaxis and/or therapy for thromboembolic events
 - Be able to understand, give written informed consent, and comply with all study-related procedures, medication use, and evaluations

- Not have a history of noncompliance in relation to medical regimens or be considered potentially unreliable and/or uncooperative
- Be able to understand the reason for complying with the special conditions of the protocol and supplemental Summary of Pregnancy Prevention Strategies and give written acknowledgement of this in the informed consent form (ICF)

6.2. Subject Exclusion Criteria

Subjects who meet any of the following criteria will be excluded from the study:

Exclusionary Diagnosis

- High-grade B-cell lymphoma, including those with MYC and BCL2 and/or BCL6 rearrangements (double-hit or triple-hit lymphoma) and high-grade B-cell lymphoma NOS, according to WHO 2016 criteria
- Any other histological type of lymphoma, including primary mediastinal (thymic) large B-cell (PMBL) or Burkitt lymphoma
- A prior diagnosis of CLL (Richter's Transformation)
- Primary central nervous system (CNS) lymphoma
- A history of secondary CNS involvement by DLBCL are ineligible, unless treated into remission

Exclusionary Previous and Current Treatment

- Subjects who have previously received treatment with an anti-CD20 × anti-CD3 bsAb
- Subjects who have been previously treated with tafasitamab
- Anti-CD20 therapy (eg, rituximab) within 21 days prior to Day –8, in order to minimize competition with plamotamab binding to CD20 on DLBCL target cells
- Subjects who have, within 14 days prior to Day –8:
 - Chemotherapy, radiotherapy, or other lymphoma-specific therapy not including anti-CD20 therapy. Note: palliative local radiotherapy is permitted; however, these lesions may not serve as target lesions.
 - Small molecule or investigational anticancer agents within 6 elimination half-lives prior to Day –8
 - Undergone major surgery not related to lymphoma complications or suffered from significant traumatic injury

- Received live vaccines (see [Section 7.2](#) for details) within 30 days of Day –8
- Required systemic anti-infective therapy for active, intercurrent infections
- Subjects who have had the following prior therapies or treatments:
 - Have, in the opinion of the Investigator, not recovered sufficiently from the adverse effects of prior therapy(ies)
 - Were previously treated with CD19-targeted therapy, including CAR-T, unless current biopsy (after last therapy) is CD19+
 - Have known intolerance to CD20 monoclonal antibody therapy
 - Have a history of hypersensitivity to compounds of similar biological or chemical composition to tafasitamab, IMiDs, and/or the excipients contained in the study drug formulations
 - Have undergone ASCT \leq 1 month prior to signing the informed consent form. Subjects who have a more distant history of ASCT must exhibit full hematologic recovery before enrollment into the study.
 - Have undergone previous allogenic stem cell transplantation
 - Have a history of deep venous thrombosis/embolism, threatening thromboembolism, or known thrombophilia, or are at high risk for a thromboembolic event in the opinion of the Investigator, and who are not willing/able to take venous thromboembolic event prophylaxis during the entire treatment period
 - Concurrently use other anticancer or experimental treatments

Exclusionary Subject’s Medical History

- Prior history of malignancies other than DLBCL, unless the subject has been free of the disease for \geq 3 years prior to screening. Exceptions to the \geq 3-year time limit include a history of the following:
 - Basal cell carcinoma of the skin
 - Squamous cell carcinoma of the skin
 - Carcinoma in situ of the cervix
 - Carcinoma in situ of the breast
 - Carcinoma in situ of the bladder

- Tumor/Node/Metastasis stage of T1a or T1b prostate cancer
- Subjects with the following medical history:
 - Known active hepatitis infection:
 - Positive test for hepatitis B surface antigen (HBsAg) or hepatitis B core antibody (HBcAb; a subject whose HBsAg or HBcAb is positive may be enrolled if a hepatitis B virus [HBV] DNA test is negative and either the subject is treated with potent antiviral therapy or is re-tested for HBV DNA every month)
 - Positive test for hepatitis C virus (HCV) antibodies (a subject whose HCV antibody test is positive may be enrolled if quantitative HCV polymerase chain reaction test is negative)
 - Known seropositivity for or history of active viral infection with human immunodeficiency virus (HIV)
 - Positive SARS-CoV-2 nucleic acid or antigen test
 - History or evidence of clinically significant cardiovascular, CNS, and/or other systemic disease that would in the Investigator’s opinion preclude participation in the study or compromise the subject’s ability to give informed consent
 - History of solid organ transplantation
 - History or evidence of rare hereditary problems of galactose intolerance, Lapp lactase deficiency, or glucose-galactose malabsorption
 - Gastrointestinal abnormalities that would interfere with the ability to take or absorb oral medication

6.3. Subject Withdrawal Criteria

6.3.1. Criteria for Removal from Study Treatment

A subject may withdraw from the study treatment at any time at his/her own request, or may be withdrawn at any time at the discretion of the Investigator for any of the following reasons:

- Disease progression
- Occurrence of an unacceptable AE
- Investigator decision
- Subject non-compliance with study drug
- Death

- Administrative reasons
- Other

Subjects must be withdrawn from treatment if the beta human chorionic gonadotropin (β -HCG) pregnancy test is consistent with pregnancy. Before permanent study treatment discontinuation, the treatment may be interrupted to confirm the positive pregnancy test. Pregnancy should be reported as described in [Section 10.4](#). Subjects with a confirmed positive pregnancy test will continue in the follow-up phase of the study.

6.3.2. Criteria for Removal from Study

The subject is considered to be off study for any of the following reasons:

- Screen failure
- Completed study follow-up period of 5 years
- Subject requests to be withdrawn from study and any follow-up
- Death

Whenever possible, the Sponsor must be notified within 24 hours if a subject is withdrawn from treatment and/or study. The reason(s) for a subject's discontinuation from the treatment and study are to be reported to the Sponsor and recorded in the source documents and the subject's eCRF. For subjects who withdraw their consent from the study, this must be clearly documented in their subject source documents with confirmation that no further follow-up and data may be collected.

The EOT and end-of-study (EOS) termination pages in the eCRF must be completed for all subjects who discontinue permanently.

For subjects who discontinue study treatment, all assessments described for the EOT visit should be performed at the scheduled visit dates (if at all possible). Subjects who complete a tumor assessment within 14 days of EOT do not have to repeat the EOT tumor assessment. Complete the EOS eCRF and any follow-up forms at the time of screen failure, death, or withdrawal of consent.

If it is possible, perform all assessments as close to the scheduled dates as is practicable. Post-treatment evaluations should attempt to be completed no later than approximately 4 weeks after the final dose administration and prior to initiation of a new treatment for the malignancy.

Subjects who are withdrawn for any reason may not re-enter this study. The Study Sponsor, Xencor, reserves the right to terminate this clinical study at any time and for any reason.

6.4. Avoidance of Pregnancy

Lenalidomide, a thalidomide analogue, caused limb abnormalities in a developmental monkey study similar to birth defects caused by thalidomide in humans. If lenalidomide is used during pregnancy, it may cause birth defects or embryo-fetal death. Pregnancy must be

excluded before start of treatment. Prevent pregnancy during treatment by the use of 2 reliable methods of contraception (USPI, Section 5.1). For the most recent information on lenalidomide, see the prescribing information in Revlimid[®] PI, 2021; Revlimid[®] SmPC, 2022.

For the most recent information on tafasitamab, refer to the US PI (Monjuvi[®] PI, 2021) or the European Medicines Agency SmPc (Minjuvi[®] SmPC, 2021).

Subjects receiving tafasitamab and/or lenalidomide should refer to their respective medication guides for more information on avoidance of pregnancy.

Female subjects and male subjects with female partners of childbearing potential must agree to use 2 highly effective methods of birth control during, and after, the last dose of study drug. Women are considered to be of childbearing potential unless there is a documented reason (ie, postmenopausal by history with no menses for 1 year and confirmed by follicle-stimulating hormone [FSH; using local reference ranges], OR history of hysterectomy, OR history of bilateral tubal ligation, OR history of bilateral oophorectomy (CTFG, 2020).

Male subjects will be followed for 6 months, and female subjects 8 months following the last dose of study drug to confirm contraceptive use. If a pregnancy occurs during this timeframe, it will be reported per guidelines in Section 10.4. A woman is considered of childbearing potential, ie fertile, following menarche and until becoming post-menopausal unless permanently sterile. Permanent sterilization methods include hysterectomy, bilateral salpingectomy and bilateral oophorectomy. A postmenopausal state is defined as no menses for 12 months without an alternative medical cause. A high FSH level in the postmenopausal range may be used to confirm a post-menopausal state in women not using hormonal contraception or hormonal replacement therapy. However, in the absence of 12 months of amenorrhea, a single FSH measurement is insufficient. A man is considered fertile after puberty unless permanently sterile by vasectomy or bilateral orchiectomy (CTFG, 2020).

Women of childbearing potential must have a negative serum or urine pregnancy test during screening, prior to starting study therapy at Day -8 and again at Cycle 1 Day 1. In addition, a negative pregnancy test is required at Day 1 of each subsequent cycle prior to study drug infusion, and women of childbearing potential must use a combination of one highly effective contraception and one effective contraception method during the study and for 8 months following last dose of plamotamab, tafasitamab, or lenalidomide (whichever is administered last).

Highly effective contraception includes the following:

- Combined (estrogen and progestogen containing) hormonal contraception associated with inhibition of ovulation: oral, intravaginal and transdermal
- Contraception methods that are considered to have low user dependency include the following:
 - Progestogen-only hormonal contraception associated with inhibition of ovulation: oral, injectable and implantable

- Intrauterine device (IUD)
- Intrauterine hormone-releasing system (IUS)
- Bilateral tubal occlusion
- Vasectomized partner
- Sexual abstinence
 - Sexual abstinence is considered a highly effective contraception method only if defined as refraining from heterosexual intercourse during the entire period of risk associated with the study treatments. The reliability of sexual abstinence needs to be evaluated in relation to the duration of the clinical trial and the preferred and usual lifestyle of the subject. The Investigator is responsible for evaluating the reliability of the subject’s ability to maintain sexual abstinence throughout the duration of the clinical trial.

Effective contraception includes the following:

- Male condom
- Diaphragm
- Cervical cap

Periodic abstinence (calendar, ovulation, symptom-thermal, post-ovulation methods) and withdrawal are not acceptable methods of contraception. Progesterone-only “mini pills,” IUD progesterone T, female condoms, and cervical shield are also not acceptable.

The male subjects must agree to use condoms.

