7.5.2. Day –8, Day –4, and Day –1

- Abbreviated PE (Day –8 and Day –1 only)
- Neurologic examination will be assessed using the ASTCT ICANS Consensus Grading for Adults (Day –1 only, see [Section 4.6.1.7](#))

- Vital signs (supine or sitting position, including heart rate, blood pressure, temperature, respiratory rate, and blood oxygen saturation by continuous pulse oximetry)
- Weight (Day –8 and Day –1)
- ECOG performance status (see [Appendix A](#))
- CBC with differential (percent and absolute) and platelet count (see [Section 7.5.1](#)) (Day –8 and Day –1 only)
- Chemistry panel (see [Section 7.5.1](#)) (Day –8 and Day –1 only)
- Fibrinogen (Day –1 only)
- Coagulation panel (PT/ INR and APTT) (Day –1 only)
- Urinalysis (see [Section 7.5.1](#)) (Day –8 and Day –1 only)
- Urine or serum β -hCG pregnancy test for women of childbearing potential (Day –8 and Day -1 only)
- The following to be sent to the central laboratory per the laboratory manual:
 - Serum sample for rituximab level (Day –1 only)
 - Serum samples for tafasitamab PK and ADA (Day –8 only)
 - Peripheral blood for TBNK, leukocyte flow cytometry (Day –8 only)
 - Peripheral blood for RNA analysis (Day –8 only, prior to tafasitamab dose)
- Administration of tafasitamab on Day –8 and Day –4
- Record concomitant medications and AEs

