Laboratory Assessments: Safety laboratory assessments, including CBC with differential, chemistry panel, fibrinogen, coagulation panel, urinalysis, and pregnancy tests, may be completed up to 24 hours prior to the visit day. Excepted is the pregnancy test prior to the first dose of lenalidomide, which should be completed on Cycle 1 Day 1, within 24 hours of initiating treatment. Safety laboratory values, except for differential counts, fibrinogen, coagulation panel, and urinalysis, should be reviewed before starting study drug infusion.

- CBC with differential (absolute and percent), platelet count, and blast count, if reported (see [Section 7.5.1](#))
- Chemistry panel (see [Section 7.5.1](#))
- Fibrinogen
- If HBcAb serology is positive, HBsAg and hepatitis B DNA testing should be performed, with results available prior to dosing, on Day 1 of Cycles 2 and later, and at EOT (unless HBsAb is also present).
- Coagulation panel (prothrombin time PT/INR and APTT)
- Urinalysis (see [Section 7.5.1](#))
- Urine or serum β -hCG pregnancy test for women of childbearing potential should occur weekly during the first 4 weeks of lenalidomide, then on Day 1 of each subsequent cycles for dosing of plamotamab, tafasitamab, or lenalidomide. If menstrual cycles are irregular, the pregnancy testing should occur every 2 weeks during each subsequent cycle.
- The following are to be sent to the central laboratory per the laboratory manual:
 - Serum samples for plamotamab and tafasitamab ADA, cytokines, and plamotamab and tafasitamab PK (see [Table 10](#) and [Table 11](#) for collection schedule). All samples should be drawn within the window indicated on [Table 9](#) and of the designated time and should be labeled with the exact, actual time of sampling.
 - Peripheral blood for TBNK, leukocyte flow cytometry
 - Peripheral blood for RNA analysis

- Peripheral blood for ctDNA analysis
- Tumor biopsies (for those subjects who provided consent) collected once at follow-up (See [Section 8.2.2](#) and [Table 9](#))

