10.4.3. Embryo-Fetal Toxicity from Lenalidomide WARNINGS AND PRECAUTIONS Section

Lenalidomide is a thalidomide analogue and is contraindicated for use during pregnancy. Thalidomide is a known human teratogen that causes life-threatening human birth defects or embryo-fetal death (see [Revlimid[®] PI, 2021](#), “Use in Specific Populations” [8.1]). An embryo-fetal development study in monkeys indicates that lenalidomide produced malformations in the offspring of female monkeys who received the drug during pregnancy, similar to birth defects observed in humans following exposure to thalidomide during pregnancy.

Women of Childbearing Potential:

Women of reproductive potential must avoid pregnancy for at least 4 weeks before beginning lenalidomide therapy, during therapy, during dose interruptions and for at least 4 weeks after completing therapy. Females must commit either to abstain continuously from heterosexual sexual intercourse or to use 2 methods of reliable birth control, beginning 4 weeks prior to initiating treatment with lenalidomide, during therapy, during dose interruptions and continuing for 4 weeks following discontinuation of lenalidomide therapy. Two negative pregnancy tests must be obtained prior to initiating therapy. The first test should be performed within 10 days and the second test within 24 hours prior to prescribing lenalidomide therapy. Thereafter, tests should occur weekly during the first month, then monthly thereafter in females with regular menstrual cycles, or every 2 weeks in females with irregular menstrual cycles.

Males:

Lenalidomide is present in the semen of subjects receiving the drug. Therefore, males must always use a latex or synthetic condom during any sexual contact with females of reproductive potential while taking lenalidomide and for up to 4 weeks after discontinuing lenalidomide, even if they have undergone a successful vasectomy. Male subjects taking lenalidomide must not donate sperm.

Blood Donation:

Subjects must not donate blood during treatment with lenalidomide and for 4 weeks following discontinuation of the drug because the blood might be given to a pregnant female subject whose fetus must not be exposed to lenalidomide.

Pregnancy Exposure Registry:

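### The pregnancy-prevention rules conflict in four places: contraceptive methods, tubal ligation, type of pregnancy test, and a Cycle 1 Day 1 test that Table 9 omits

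*Protocol*

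**What the plan says.** All references are to the Protocol unless stated.

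- **Methods.** Section 6.4 first says that female subjects, and male subjects whose partners could become pregnant, "must agree to use 2 highly effective methods of birth control during, and after, the last dose of study drug". Further on it says that women of childbearing potential "must use a combination of one highly effective contraception and one effective contraception method". The inclusion criterion in Section 6.1 has a third wording, "by using 2 different methods of birth control with at least 99% certainty", with continuous abstinence as the alternative, and sends the reader to Section 6.4 for the permitted methods.
- **Who counts as fertile.** Section 6.4 lists documented reasons for treating a woman as not of childbearing potential, among them "OR history of bilateral tubal ligation". Later in the section: "Permanent sterilization methods include hysterectomy, bilateral salpingectomy and bilateral oophorectomy". Bilateral tubal occlusion then appears in its list of contraceptive methods.
- **Test type.** Section 6.1 requires a negative serum test at screening and again before the first lenalidomide dose. Sections 6.4, 7.5.1 and 7.6.1 allow urine or serum.
- **Test at the start of lenalidomide.** Section 6.1 requires a test before the Day 1 dose, within 24 hours. Section 6.4 asks for one at Cycle 1 Day 1. Section 7.6.1 lets safety laboratory tests be done up to a day before the visit but excepts this one, "which should be completed on Cycle 1 Day 1, within 24 hours of initiating treatment". The pregnancy-test row of Table 9 has a mark at Day −1 and none at Cycle 1 Day 1. A Table 9 footnote places lenalidomide dosing in the evening, from Day 1.

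**The concern.** Section 10.4.3 describes lenalidomide as a thalidomide analogue that must not be used in pregnancy, and both arms receive it. Safeguards of this kind work only if a site can tell who is covered, what she must use, which test counts and when it is due. On each of these the Protocol gives two answers.

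The consequences are concrete. A woman with a tubal ligation is either outside the testing and contraception rules or inside them, depending on the sentence read. A pair of methods can satisfy one sentence of Section 6.4 and fail another. A site that works from the schedule of assessments would find no pregnancy test listed for the day lenalidomide starts.

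**Working it through.** No figure in the plan is to be reproduced. The check sets the passages side by side, reads one row of Table 9, and does one clock calculation.

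**1. Methods.** Both sentences of Section 6.4 apply to women of childbearing potential. The section lists two classes: the intrauterine device is in the highly effective class, and the diaphragm is in the effective class. An intrauterine device plus a diaphragm meets the one-plus-one rule and fails the two-highly-effective rule. The cross-reference from Section 6.1 does not help, because it leads to the section that contains the conflict.

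**2. Tubal ligation.** The first definition removes a woman with a ligation from childbearing potential. The second names three sterilization procedures, and ligation is not among them. Listing tubal occlusion as contraception presupposes a user who still counts as fertile. The first definition points one way and the other two statements point the other way.

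**3. Test type.** A urine result satisfies Sections 6.4, 7.5.1 and 7.6.1 and does not satisfy Section 6.1.

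**4. Test timing.** The Table 9 row, read against its day header:

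| Day | Mark |
|---|---|
| Screening | X |
| Day −8 | X |
| Day −4 | blank |
| Day −1 | X |
| Cycle 1 Day 1 | blank |
| Cycle 1 Days 2, 3, 4 | blank |
| Cycle 1 Days 8, 15, 22 | X |
| Cycle 2 Day 1 | X |

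The lenalidomide counseling row of the same table does carry a mark at Cycle 1 Day 1, so a column shift in the extracted text is unlikely.

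Section 7.6.1 says that Day −1 is the day before Cycle 1 Day 1, so there is no Day 0. If the test is at clock time *t* on Day −1 and the dose at clock time *d* on Day 1, then

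interval = 24 + *d* − *t* hours.

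The Protocol says only that dosing is in the evening. I assume *d* between 18:00 and 22:00 and let *t* be any time on Day −1:

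- shortest: 24 + 18 − 24 = 18 hours
- longest: 24 + 22 − 0 = 46 hours
- a morning test at 08:00 with a 20:00 dose: 24 + 20 − 8 = 36 hours

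The interval is 24 hours or less only when *t* is at or after *d*, that is, when the Day −1 test is taken no earlier in the day than the next day's dose. Such a late test would meet the 24-hour limit in Section 6.1. It would still not be a Cycle 1 Day 1 test as Sections 6.4 and 7.6.1 require.

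**The case against.** The other side has several fair points.

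- **The text on timing agrees with itself.** Three sections call for the test at lenalidomide start, and Section 5 refers readers to the protocol text for detail beyond the tables. The fault is one empty cell, and a site that reads the text would do the test. That stands. It is why the claim is that a site using Table 9 alone could miss the window, and not that it would. The 36-hour figure depends on assumed clock times.
- **Section 7.5.2.** A reader might infer from its "Day –8 and Day –1 only" restriction that a Cycle 1 Day 1 test is ruled out. It is not. That section covers the pretreatment days only, so the restriction excludes Day −4 and says nothing about Cycle 1. The timing conflict rests on Table 9.
- **Duration.** A reader might also see a flat contradiction between 8 months of contraception for women (Sections 6.1 and 6.4) and the 4 weeks in Section 10.4.3. The documents do not support that reading. Section 10.4.3 is specific to lenalidomide and says "for at least 4 weeks after completing therapy", a minimum that 8 months satisfies. What remains is a labelling problem: the 8-month rule in Section 6.4 names lenalidomide too, and for men Section 10.4.3 says up to 4 weeks where Section 6.1 says 180 days.
- **The sterilization list may not be exhaustive.** Its verb is open-ended, so ligation might be implied. That is hard to hold alongside the listing of tubal occlusion as contraception.
- **A separate pregnancy-prevention summary exists.** Sections 6.1, 7.5.1 and 7.6.1 refer to it. It is not among the documents, so its effect on sites is unknown, and it cannot make the Protocol's own text consistent.
- **No statistical consequence, and the trial has stopped.** Both are true. They lower the urgency and do not remove the conflicts.

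**Conclusion.** Four contradictions stand on the text: two highly effective methods against one highly effective plus one effective; tubal ligation as an exemption against its absence from permanent sterilization and the listing of tubal occlusion as contraception; serum only against urine or serum; and a required Cycle 1 Day 1 test against a blank cell in Table 9.

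The first three need no assumption. The timing gap of about 18 to 46 hours assumes an evening dose between 18:00 and 22:00 and a test at any time on Day −1. The blank cell itself does not depend on those times.

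The matter is one of patient and fetal safety and of site conduct. It does not touch the estimand, the sample size or any analysis. The SAP (Sections 1, 4.1 and 7) reports early termination with 3 subjects enrolled, which limits the practical impact. The conflicts would carry over if the text were reused.

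**What to change.** Reconcile Sections 6.1, 6.4, 7.5.1 and 7.6.1 and Table 9 so that they state one method requirement, one definition of childbearing potential and one test type. Make the Table 9 timing agree with the Cycle 1 Day 1 text. The synopsis repeats the Section 6.1 criteria and should follow. Which rule stands on each point is for the sponsor to decide.

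As a minor addition, label the 4-week periods in Section 10.4.3 as specific to lenalidomide, or reconcile them with the 8-month and 180-day trial rules.

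The cost is protocol wording and one schedule cell. No analysis changes.
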